7.1.3 Inclusion for Participants with Hepatic Impairment and Healthy Participants

Participants must fulfill the following inclusion criteria to be eligible for participation in the study:

1. Understands the study procedures in the ICF, provides a signature/date in the ICF, and is willing and able to comply with the protocol.
2. Continuous non-smoker or moderate smoker (≤ 10 cigarettes/day or the equivalent) before screening. Participant must agree to consume no more than 5 cigarettes or equivalent/day from the 7 days prior check-in and until discharge from the CRU.
3. Female participants of childbearing potential and male participants agree to comply with any applicable contraceptive requirements of the protocol as detailed in [Appendix D](#).

7.2 Exclusion Criteria

7.2.1 Exclusion for Participants with Hepatic Impairment

The participant must be excluded from participating in the study if the participant:

1. Has history or presence of clinically significant medical or psychiatric condition or disease (aside from HI) or presence of psychotic disorders such as psychosis, delusions, or schizophrenia in the opinion of the Investigator or designee.
2. Has a history of liver or other solid organ transplant.
3. Has history or presence of alcoholism and drug abuse within the past 6 months prior to dosing.
4. Positive result at screening for HIV. HBsAg positive participants are allowed to be enrolled if HBV DNA is below 1000 copies/mL in the plasma. Participants with moderate or mild HI who are positive for HCVAb can be enrolled but must not have detectable HCV RNA in the plasma.

7.2.2 Exclusion for Healthy Participants

The participant must be excluded from participating in the study if the participant:

1. Has history or presence of clinically significant medical or psychiatric condition or disease or presence of psychotic disorders such as psychosis, delusions, or schizophrenia in the opinion of the Investigator or designee.
2. Has history or presence of alcoholism and drug abuse within the past 2 years prior to dosing.
3. Positive results at screening for HIV, HBsAg, or HCV.

7.2.3 Exclusion for Participants with Hepatic Impairment and Healthy Participants

The participant must be excluded from participating in the study if the participant:

1. Has history of any illness that, in the opinion of the Investigator or designee, might confound the results of the study or poses an additional risk to the participant by their participation in the study.
2. Has history or presence of clinically significant hypersensitivity or idiosyncratic reaction to the study drug or related compounds.
3. Has positive results for the urine or saliva drug screen at screening or check-in, unless the positive drug screen is due to prescription drug use that is approved by the Investigator (cannabinoids can be used for medicinal use at the discretion of the Investigator).
4. Is a female with a positive pregnancy test or who is lactating.
5. Has positive results for urine or breath alcohol screen at screening or check-in.
6. Is unable to refrain from or anticipates the use of any medication or substance (including prescription or over-the-counter, vitamin supplements, natural or herbal supplements) as indicated in Section 7.3 (Excluded Medications, Supplements, Dietary Products) for the prohibited time period.

7. Has been on a diet incompatible with the on-study diet, in the opinion of the Investigator or designee, within the 30 days prior to dosing.
8. Has made a donation of blood or had significant blood loss within 56 days prior to dosing.
9. Has made a plasma donation within 7 days prior to dosing.
10. Participated in another clinical study within 30 days prior to dosing. The 30-day window will be derived from the date of the last dosing in the previous study to Day 1 of the current study.
11. Any positive responses on the C-SSRS or has a risk of suicide according to the Investigator's judgment based on the assessment of the C-SSRS at screening or check-in or has made a suicide attempt in the previous 12 months prior to dosing.

7.3 Excluded Medications, Supplements, Dietary Products

Healthy participants will be restricted of using any prescription medications/products and any over-the-counter, nonprescription preparations (including herbal products, natural or herbal supplements) from at least 14 days before dosing and throughout the study. However, healthy participants that are on stable medication for at least 30 days prior to dosing may be enrolled upon approval by the Investigator (or designee) and Sponsor.

Participants with HI who are taking medications to treat manifestations of hepatic disease or medications needed to treat for stable diseases (e.g., diuretics, angiotensin converting enzyme inhibitors, angiotensin II receptor antagonists, and beta-blockers) will be allowed to participate in the study at the discretion of the Investigator and following consultation with the Sponsor. For hepatic disease related medical conditions, participants must be on a stable dose (steady dose, drug, and regimen) for at least 30 days and/or for non-hepatic disease related medical conditions for 14 days before dosing and able to withhold the use for at least 4 hours postdose. Phosphate binders containing aluminum, calcium, or lanthanum salts; iron supplements or other metal cations; H2-receptor antagonists (except cimetidine); or multivitamins containing iron or zinc must be withheld at least 8 hours before dosing and at least 4 hours postdose.

If a participant with HI is prescribed prohibited medication, upon discussion between the sponsor and the Investigator, the Investigator may substitute the previously prescribed medication to an allowed one for the purpose of this study.

For all participants, any drugs known to be strong inhibitors or inducers of CYP3A, UGT1A9 or UGT2B4, including St. John's Wort, will be restricted for 14 days or 28 days, respectively, before dosing and throughout the study. Use of moderate and weak inhibitors or moderate and weak inducers may be deemed acceptable following consultation with the sponsor and the Investigator or designee. Appropriate sources (e.g., Flockhart TableTM) will be consulted to confirm lack of PK/PD interaction with study drug. Cannabinoids can be used for medicinal use at the discretion of the Investigator.

For all participants, following dosing, acetaminophen (up to 2 g per 24 hours) may be administered at the discretion of the Investigator or designee.

Any medication (including over-the-counter) that would significantly alter creatinine clearance, which, by the determination of the Investigator, might interfere with the study (e.g., cimetidine) must be discontinued at least 2 weeks prior to dosing and throughout the study.

All medications taken by participants during the course of the study will be recorded.

Concurrent medication during the course of the study including both prescription and non-prescription drugs may be permitted based on the timing of study drug administration and its pharmacology, but must first be discussed with the Investigator or designee and sponsor prior to dosing, unless appropriate medical care necessitates that therapy should begin before the Investigator or designee and sponsor can be consulted.

If deviations occur, the Investigator or designee in consultation with the Sponsor if needed will decide on a case by case basis whether the participant may continue participation in the study based on the time the drugs were administered and their pharmacology.

Use of excluded agents (prescription or non-prescription) or dietary products is outlined in [Table 7.a](#).

Table 7.a Excluded Medications, Supplements, and Dietary Products

Category	Between Screening and First Dosing (Days -28 to Predose [Day 1])	After Dosing (Day 1) to Discharge (Day 7)
Alcohol	Prohibited from 48 hours prior to dosing	Prohibited from dosing until discharge from CRU completed.
Xanthine and/or caffeine	Prohibited from 24 hours prior to dosing ^a	Prohibited from dosing until discharge from CRU completed. ^a
Medications	See Section 7.3	See Sections 7.3
Food substance		
Grapefruit/Seville orange	Prohibited from 14 days prior to dosing	Prohibited from dosing until discharge from CRU completed.
Nicotine and analogous derivatives	≤ 5 cigarettes/day 7 days prior to dosing	≤ 5 cigarettes/day until discharge from CRU completed.

(a) small amounts of caffeine derived from normal foodstuffs e.g., 250 mL/8 oz./1 cup decaffeinated coffee or other decaffeinated beverage, per day, with the exception of espresso; 45 g/1.5 oz. chocolate bar, per day, would not be considered a deviation to this restriction.

7.4 Diet, Fluid, Activity

7.4.1 Diet and Fluid

Water (except water provided with dosing) will be restricted 1 hour prior to and 1 hour after dosing, but will be allowed ad libitum at all other times, when dosing occurs at the CRU. Other fluids may be given as part of meals and snacks but will be restricted at all other times throughout the confinement period.

Participants will fast overnight for at least 10 hours prior to dosing. Participants will continue the fast for at least 4 hours postdose.

When confined, standard meals and snacks will be provided at appropriate times, except when they are required to fast. When confined in the CRU, participants will be required to fast from all food and drink except water between meals and snacks.

7.4.2 Activity

All participants will remain seated for the first 4 hours following dosing, except when they are supine or semi-reclined for study procedures. Participants will then resume normal activity.

However, should AEs occur at any time, participants may be placed in an appropriate position or will be permitted to lie down on their right side. During the first 4 hours postdose, participants may be allowed to rise for brief periods under supervision (e.g., in order to use the toilet facilities).

Participants will be instructed to refrain from strenuous physical activity which could cause muscle aches or injury, including contact sports at any time from screening until completion of the study.

Participants must not consume more than 5 cigarettes or equivalent/day from the 7 days prior to check-in and until discharge from the CRU. Depending on the CRU rules and regulations, participants may be prohibited from smoking during their confinement or during portions of their confinement.

7.5 Criteria for Discontinuation or Withdrawal of a Participant

The primary reason for discontinuation or withdrawal of the participant from the study or study drug should be recorded in the case report form (CRF) using the following categories.

1. Pretreatment event (PTE) or AE: The participant has experienced a PTE or AE that requires early termination because continued participation imposes an unacceptable risk to the participant's health or the participant is unwilling to continue because of the PTE or AE.

Liver Function Test (LFT) Abnormalities

Appropriate clinical follow-up will be conducted (including repeat laboratory tests, until a participant's laboratory profile has returned to normal/baseline status, see Section 9.2.9.1), if the following circumstances occur at any time following study drug treatment:

- ALT or AST >8 x ULN, or
- ALT or AST >5 x ULN with appearance of fatigue, nausea, vomiting, right upper quadrant pain or tenderness, fever, rash and/or eosinophilia ($>5\%$).

QTcF interval:

Appropriate clinical follow-up will be conducted if a QTcF interval >500 msec and/or an increase from baseline > 60 msec is detected by ECG and confirmed with a repeat ECG at any time following study drug treatment. Appropriate clinical follow-up includes a repeat ECG.

2. Significant protocol deviation: The discovery post-enrollment that the participants failed to meet protocol entry criteria or did not adhere to protocol requirements, and continued participation poses an unacceptable risk to the participant's health.
3. Lost to follow-up: Attempts to contact the participants were unsuccessful. Attempts to contact the participant must be documented in the participant's source documents.
4. Voluntary withdrawal: The participants (or participant's legally acceptable representative) wish to withdraw from the study. The reason for withdrawal, if provided, should be recorded in the CRF.

Note: All attempts should be made to determine the underlying reason for the withdrawal and, where possible, the primary underlying reason should be recorded (ie, withdrawal due to an AE should not be recorded in the "voluntary withdrawal" category). If a participant chooses to withdraw from study participation due to personal concerns related to the COVID-19 pandemic (other than a COVID-19-related AE), this should be specified as the reason for participant withdrawal in the CRF.

5. Study termination: The Sponsor, IRB/ IEC, or regulatory agency terminates the study.
6. Pregnancy: as described in [Appendix D](#).
7. Participants may be withdrawn from the study by the Investigator or designee for the following reasons:
 - Difficulties in blood collection.
 - Positive urine drug or alcohol test.

Other: The specific reasons for discontinuation should be entered into the CRF including unavoidable circumstances such as the COVID-19 pandemic. Participants may be withdrawn from the study at any time at the discretion of the Investigator or sponsor for safety reasons which should be entered into the CRF.

7.6 Procedures for Discontinuation or Withdrawal of a Participant

The Investigator may discontinue a participant's study participation at any time during the study when the participant meets the study termination criteria described in Section [7.5](#). In addition, a participant may discontinue his or her participation without giving a reason at any time during the study. Should a participant's participation be discontinued, the primary criterion for termination must be recorded by the Investigator. In addition, efforts should be made to perform all procedures scheduled for the end-of-study or early termination as described in Section [3.0](#).

7.7 Participant Replacement

Replacement of discontinued or withdrawn participants due to any reason will be assessed on a case by case basis by the sponsor and Investigator. Any participant who is not PK evaluable including those experiencing emesis within 8 hours post dose may be replaced at the discretion of the Investigators in consultation with the sponsor to ensure 8 PK-evaluable participants in each

arm of participants with HI and 12-24 PK-evaluable participants in matched participants with normal hepatic function complete.

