9.3.1 PK Measurements

Samples from all participants will be assayed even if the participants do not complete the study. Samples for determination of plasma soticlestat [REDACTED] will be analyzed using validated bioanalytical methods.

Pharmacokinetic parameters of soticlestat [REDACTED] will be calculated from the individual concentration-time profiles from all evaluable participants using noncompartmental analysis methods. Actual sampling times, rather than scheduled sampling times, will be used in all computations involving sampling times.

The fraction of unbound soticlestat will be determined.

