5.2 Pharmacokinetic Analysis Set

All participants who comply sufficiently with the protocol and display an evaluable PK profile (eg, exposure to treatment, availability of measurements and absence of major protocol violations) will be included in the statistical analyses.

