6.0 STATISTICAL ANALYSIS

6.1 General Considerations

All PK analyses will be conducted using Phoenix® WinNonlin® Version 8.1, or higher. All statistical analyses will be conducted using SAS® Version 9.4. All data recorded on the case report form (CRF) will be listed by hepatic function group and participant. All table, figure, and listing (TFL) shells and numbering list will be included and specified in the TFL Shells document.

The number of observations (n) will be presented as an integer (no decimal places), arithmetic mean (mean), median, and geometric mean (geom mean) values will be presented to 1 more level of precision than the individual values. Standard deviation (SD) and standard error of the mean (SEM) will be presented to 2 more levels of precision than the individual values. Minimum and maximum values will be presented to the same precision as the individual values. Arithmetic percent coefficient of variation (CV%) and geometric percent coefficient of variation (geom CV%) will be presented to 1 decimal place.

Geometric least-squares means (LSMs) will be reported with 1 more level of precision than the individual data. Geometric mean ratios (GMRs) and 90% confidence intervals (CIs) for the GMRs will be reported using 2 decimal places.

Noncompartmental analyses will be used in this study. Concentration values below the lower limit of quantitation (BLQ) will be presented as 'BLQ' in the concentration table listings and footnoted accordingly. BLQ values will be treated as zero for the calculation of summary statistics, the generation of concentration plots, and the calculation of PK parameters, unless they are deemed questionable (e.g., BLQ value between measurable values), in which case they will be treated as missing and excluded from the concentration summary statistics and the PK analysis. Values of 0 are not included in the calculation of geom mean and geom CV%.

A participant's PK parameter data will be included in the listings but may be excluded from the descriptive and inferential (linear mixed-effects model) statistics if one or more of the following criteria are met:

- A predose (0 hour) concentration is greater than 5% of that participant's maximum concentration value for the given hepatic function group
- A participant did not meet inclusion/exclusion criteria that may have an effect on the PK (as determined by the Takeda Pharmacology Lead and Celerion Pharmacokinetic Scientist)

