- A participant deviates substantially from the protocol defined study procedures including but not limited to dosing, dose timing, sample collection, meal timing, etc. (as determined by the Takeda Clinical Pharmacology Lead and Celerion Pharmacokinetic Scientist)
- A participant may be excluded due to vomiting

The details on PK parameter calculations and TFLs will be outlined in the clinical pharmacology and analysis plan (CPAP) and TFL Shells document including specifics on the following:

- For participants with $AUC_{\text{extrap}}\%$ greater than 20%, the descriptive and model-based statistics for AUC_{∞} will be presented with and without these participants included, if appropriate
- PK parameters presented by hepatic function group, including the units, precision, and summary statistics that will be presented in in-text and end-of-text tables
- Concentration data presented by hepatic function group, including the units, precision, and summary statistics that will be presented in end-of-text tables
- Concentration data file used for PK analysis
- PK parameter Phoenix[®] WinNonlin[®] output file used to generate the TFLs
- ANOVA model results presented in in-text and end-of-text tables
- Arithmetic mean concentration-time figures presented as in-text and end-of-text figures

- Individual concentration-time figures presented in Appendix 16.2.6.

Fraction unbound will be calculated based on the ratios of unbound concentration relative to total concentration at 0.5 and 10 hours postdose for each subject as follows:

$F_u = C_{u,0.5\text{ hrs}}/C_{0.5\text{ hrs}}$ and $F_u = C_{u,10\text{ hrs}}/C_{10\text{ hrs}}$ (where $C_u =$ unbound concentration in plasma at time t and $C_t =$ total concentration in plasma at time t).

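### Do the 8-hour emesis wording and the open-ended vomiting exclusion let sound PK profiles be dropped at will?

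*Protocol*

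**What the plan says.** Protocol 7.7, repeated in Protocol 1.0 and 11.3 and SAP 4.0, provides that "Any participant who is not PK evaluable including those experiencing emesis within 8 hours post dose may be replaced". The Investigators decide in consultation with the sponsor, and the stated purpose is to finish with 8 PK-evaluable participants in each HI arm and 12 to 24 in the normal-function arm.

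The analysis set is defined elsewhere. SAP 5.2 takes in "All participants who comply sufficiently with the protocol and display an evaluable PK profile", as does Protocol 11.1.1.1; neither mentions emesis or 8 hours. Protocol 9.3.1 says PK parameters "will be calculated from the individual concentration-time profiles from all evaluable participants using noncompartmental analysis methods", and also that "Samples from all participants will be assayed even if the participants do not complete the study".

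SAP 6.1 keeps every participant's PK parameters listed. Its exclusion clause reads: "may be excluded from the descriptive and inferential (linear mixed-effects model) statistics if one or more of the following criteria are met". There are four criteria. The first is numeric (predose concentration above 5% of the maximum). The next two, on eligibility and on procedural deviations, name the deciding roles; the wording for deviations is "as determined by the Takeda Clinical Pharmacology Lead and Celerion Pharmacokinetic Scientist". The fourth says only: "A participant may be excluded due to vomiting".

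SAP 6.8 adds that excluded parameters are shown and footnoted in the listings.

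**The concern.** The vomiting criterion is the only one of the four with neither a threshold nor a named decider, and it does not point back to the 8-hour wording in SAP 4.0. Because that wording treats emesis within 8 hours as a case of not being PK evaluable, and both Protocol 9.3.1 and the PK set rely on evaluability, the label could carry over from replacement into the primary analysis. No reason for 8 hours is given, although an immediate-release tablet is taken fasting and the documented tmax is well under an hour.

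The study is open-label, one participant is 12.5% of an HI arm, and nothing says the decision is made without sight of that participant's concentrations. If vomiting went with high exposure, removing those who vomit from an HI arm would understate the HI-to-normal ratio, on which dosing advice will rest.

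**Working it through.** The plan has no power or sample-size figure to reproduce: the HI arm size is expressly not power-based (Protocol 11.3).

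**1. Window against tmax** (Protocol 4.1.1.2)
- Single dose, fasted, healthy, median 0.25–0.52 h: 8/0.52 = 15.4 and 8/0.25 = 32.
- Japanese study, 0.5–0.75 h: 8/0.75 = 10.7 and 8/0.5 = 16.
- No tmax in HI is given.

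**2. Dose still unabsorbed at the time of emesis.** Assume a one-compartment model with first-order absorption: fraction unabsorbed = exp(−ka·t), with ka solved from tmax = ln(ka/ke)/(ka − ke).

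Two half-life bases are needed. With terminal half-lives of 4.39–8.695 h, 0.89·exp(−ke·1.5) predicts a fed/fasted Cmax ratio of 0.70–0.79, and 1/(1 − exp(−12·ke)) predicts twice-daily accumulation of 1.18–1.62. The documented figures are 0.40 (Cmax down 60%) and below 1.06. Solving 0.89·exp(−ke·1.5) = 0.40 gives ke = 0.533/h, an effective half-life of 1.30 h.

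| tmax | Half-life | 1.5 h | 4 h | 8 h |
|---|---|---|---|---|
| 0.75 h (longest documented) | 4.39–8.695 h | 0.02–0.09% | about 0 | about 0 |
| 0.75 h | 1.30 h | 1.8% | 0.002% | about 0 |
| 2.25 h (assumed: 0.75 + the 1.5 h fed delay) | 4.39–8.695 h | 14–24% | 0.5–2.1% | under 0.05% |
| 2.25 h (assumed) | 1.30 h | 58% | 23% | 5.3% |

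At healthy-participant tmax, late emesis should leave the profile intact. If HI slowed absorption to the assumed extent, 8 hours would be a cautious margin. The documents do not say which row applies to HI.

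**3. Effect of one exclusion on the ratio.** The ln-SD is not in the documents; 0.4, 0.6 and 0.8 are assumed. The expected maximum of 8 standard normals is 1.4236.
- Highest HI value removed and replaced: shift 1.4236/8 = 0.1780 SD, so exp(−0.1780·SD) = 0.931, 0.899, 0.867.
- Removed, not replaced: 1.4236/7 = 0.2034 SD, giving 0.922, 0.885, 0.850.
- Interim moderate-HI AUC∞ ratio of 299.38% (Protocol 4.2), with replacement: 279%, 269%, 260%.
- The same rule covers the normal arm. If the highest of 12 were also removed and replaced, its shift is 1.6292/12 = 0.1358 SD. The net is 0.1780 − 0.1358 = 0.0422 SD, a fall of 1.7%, 2.5% or 3.3%.
- The direction can reverse. Removing one value at half the geometric mean of the other 7 changes the arm mean by 0.5^(−1/8) = 1.091; one at twice that mean, by 2^(−1/8) = 0.917.

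**4. Against the reported interval.** SAP 6.8 estimates variance separately by group. With equal SDs and Satterthwaite degrees of freedom (assumed, as the SAS code is not shown), 8 versus 12 gives df = 15.2, t = 1.752 and SE = SD·√(1/8 + 1/12) = 0.456·SD. The 90% CI factor exp(1.752·0.456·SD) is 1.38, 1.62 or 1.90. For 7 versus 12 it is 1.40, 1.66 or 1.96.

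The worst-case shifts correspond to factors of 1/0.931 = 1.07, 1/0.899 = 1.11 and 1/0.867 = 1.15, all well inside. If vomiting is unrelated to exposure there is no bias, and the cost is the small widening from 8 to 7.

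**The case for a change.** The strongest case for acting is that this rule touches the primary endpoints and would be cheap to tighten. SAP 6.1 already has the means: named deciders for the neighbouring criteria, and, where the extrapolated AUC exceeds 20%, AUC∞ statistics that "will be presented with and without these participants included, if appropriate". Extending both to vomiting would need a line of text and one model run. SAP 6.1 leaves PK calculation details to the clinical pharmacology analysis plan, which is not supplied, but none of the items it lists for that plan is a vomiting rule. Listing an excluded value does not put it back into the geometric mean ratio.

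What stands is that SAP 6.1 is silent on window and decider, that no reason for 8 hours appears, and that sight of concentrations is not addressed.

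What does not stand is the step from silence to harm. No passage says that emesis at, say, 7 hours removes a participant from the ANOVA. The discretion runs both ways: it could equally keep a profile cut short by early vomiting. Setting the window as a multiple of healthy-participant tmax has no support in the documents for HI, and a mandatory cut would also remove profiles shown to be sound. An added with-and-without display would be extra information, not the correction of an error.

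**Conclusion.** No change is needed. The SAP leaves a detail open; it does not contradict the protocol or direct analysts to a wrong result. The roles named in the adjacent criteria are the natural ones to judge vomiting too, and they can weigh its timing against the observed profile.

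Any exclusion would be visible. Samples are assayed regardless, and SAP 6.1 and 6.8 keep excluded parameters listed and footnoted. As hepatic function group is the only fixed effect in the main model, a reader can recompute the ratio of geometric means with the participant restored. Should parameters not be calculated for someone judged not evaluable under Protocol 9.3.1, the assayed concentrations would still allow it.

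The size is bounded by a constructed worst case: a 7–13% fall with replacement, or 8–15% without, against CI factors of 1.38–1.90. These figures rest on the assumed ln-SDs, on one exclusion that happens to be the highest HI value, and on the normal arm being untouched. No emesis rate and no relation between emesis and exposure is documented, so bias is possible but not shown. The study is descriptive, with no hypotheses or decision rules (SAP 3.1 and 3.2), so no pass/fail conclusion turns on a shift of this size.
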